IRB00097529

NCT03795753

Determining the benefits of improving communication in BPAP/CPAP users

Principal Investigator: [name]

Date 03/27/2019

Minimal Risk Protocol

- 1. Protocol Title
- 2. Objectives
- 3. Background
- 4. Study Design
- 5. Study Population
 Number of Subjects
 Inclusion and Exclusion Criteria
 Inclusion
 Exclusion
 Vulnerable Populations
 Setting
 Recruitment Methods
 Consent Process
 6. Procedures
 7. Data and Specimens
- 8. Data Analysis
- 9. Privacy, Confidentiality and Data Security
- 10. Risks and Benefits
 - Risks to Subjects

Adverse events

Potential Benefits to Subjects

11. Disclosures

References

1. Protocol Title

Determining the benefits of improving communication in BPAP/CPAP users

2. Objectives

The purpose of this study is to determine the effectiveness of a non-invasive communication aid for BPAP/CPAP masks. This study also looks to determine the potential impact of the device on patients with obstructive sleep apnea (OSA) and the individuals that interact with the device.

The hypothesis is as follows: The non-invasive communication aid for patients receiving BPAP/CPAP therapy will deliver clear and effective communication between the patient and medical personnel. Furthermore, the device will increase the patient's efficacy at communicating with others.

3. Background

Non-invasive positive pressure ventilation (NIPPV) is a crucial tool used to treat respiratory distress and failure, especially in acute exacerbations of COPD. ¹ Approximately 15-24 million US citizens have COPD. ^{2,3} Of these patients, acute exacerbations of COPD accounted for almost 700,000 hospitalizations in 2010, and are expected to increase annually. Exacerbations are dangerous - with mortality rates ranging from 2.5% to 28%, depending on severity - and expensive - with costs contributing to the \$32.1 billion spent annually on COPD. ^{3,4}

Current medical practice acknowledges that treating respiratory distress and preventing respiratory failure is a paramount concern. Given the nature of the NIPPV mask, communication impairment is a commonly accepted sacrifice to maintain a patient's respiratory condition. Anecdotally, the history and physical examination of a new patient comprises the majority of the data gathering necessary for making medical decisions. Communication is critical to providing context.

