However, there is a growing body of work that indicates that limited communication can both increase length of stay and readmission rates. We can extrapolate such information from studies of communication limitations due to language barriers. For patients with language barriers, a 3-year retrospective study indicated that the absence of a professional interpreter on just admission and discharge alone significantly increased length of stay by 1.5 days and readmission rates by 63% (absolute increase 9.4%). ⁵

We will therefore study the benefit that improved communication can provide for patients on

NIPPV.

4. Study Design

This is a single-blinded, randomized control trial.

The device tested will be referred to as a "communicator".

Every patient will be consented. If accepted, we will proceed. Each patient's partner will also be consented. Demographics, including age, race, duration of BPAP/CPAP therapy, will be collected at this time.

Block randomization will be used with variable block sizes of three and six. This guarantees that the 2:1 ratio is closely maintained throughout the trial. Sealed envelopes will be utilized, with "disable" being the placebo and "enable" being the treatment. The subjects are numbered from 1 to 42. If we randomize only 30 subjects, we will have 20 enable and 10 disable. If we have 30 subjects, then the power is 70%.

One interim analysis will be undertaken after fifteen subjects are evaluated for the primary prepost outcome. The O'Brien-Fleming stopping rule will be used with a Type I error rate of 0.05.

Based upon the randomization envelope, we will randomize patients to the communicator or no-communicator arm. The study consenter will turn the device on if randomized to the

Version Date: 27 Mar 2019

communicator and disable the device if randomized to the no-communicator arm. In both situations, the device will appear outwardly similar (i.e. power lights will still appear to be on).

The study will be conducted in three phases:

- without the mask on, and
- with the mask on and without the communicator attached, and
- with the mask on and with the communicator attached.

We will recruit patients with both full face mask and nasal mask.

All patients will be issued a single-use hose and full face mask for the duration of the study. Mask fit will be determined by standard templates.

For all patients for the duration of the trial, we will provide a constant pressure of 10 cm H2O when on NIV.

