 - d. Words and sentences will be provided to the patient and the partner to learn how intelligible the patient is at baseline, without the BPAP/CPAP mask on. The patient will read each of the words and sentences at most twice total and the guest will attempt to either identify or write down what is heard.
 - e. A survey will be provided to evaluate the "mask off" stage

- f. The patient will then wear the BPAP/CPAP mask without the communicator and turn on the BPAP/CPAP machine. Patient will be instructed to use their home settings.
- g. Patients will be asked to speak normally with the same volume and effort they used in the mask off phase.
- h. The partner will subsequently ask the patient to read a new set of trial words and sentences, with the partner again trying to identify or write down the spoken content. During this period, the study coordinator will show a sign to the patient to remind them to avoid overenunciating or overpronouncing words, and to avoid raising their voice.
- i. The patient will subsequently read a new set of words and sentences, with the guest again trying to identify or write down the spoken content.
- j. A survey will be provided to evaluate the "mask on, communicator off" stage
- k. The patient will then wear the BPAP/CPAP mask, with the communicator attached.
- I. The patient will subsequently read a new set of words and sentences, with the guest again trying to identify or write down the spoken content.
- m. A survey will be provided to evaluate the "mask on, communicator on" stage
- 7. Chart review of the patients.
- 8. Study judges blinded to the phase and study arm will transcribe the recorded audio.

7. Data and Specimens

Sharing of Results with Subjects

No lab tests or genetic tests will be performed. Study results will not be shared with subjects or their providers.

8. Data Analysis

Two-tailed parametric tests will be performed on the de-identified data to compare each arm to determine superiority. The primary goal of this study is to determine effect size and observe device usage.

Likert scales will be compared across patients and partners using a nonparametric test.

Randomization

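### Should the O'Brien-Fleming look at 15 subjects be removed, or its boundary rewritten, because effect size is the stated primary goal and the maximum could be read as 30 or 42?

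*Combined protocol and SAP*

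**What the plan says.** Section 8 (Data Analysis) gives two aims in adjacent sentences: "Two-tailed parametric tests will be performed on the de-identified data to compare each arm to determine superiority", and then "The primary goal of this study is to determine effect size and observe device usage". Section 2 (Objectives) adds "The purpose of this study is to determine the effectiveness of a non-invasive communication aid for BPAP/CPAP masks".

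Section 4 (Study Design), repeated in Section 8, sets the look: "One interim analysis will be undertaken after fifteen subjects are evaluated for the primary prepost outcome". For the boundary it names O'Brien-Fleming and says that this "stopping rule will be used with a Type I error rate of 0.05". Neither section gives boundary values, the version of the boundary, its direction, or how an effect is reported after a stop.

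On size, Section 5a plans about 30 volunteers at 2:1. Sections 4 and 8 say "The subjects are numbered from 1 to 42", then "If we randomize only 30 subjects, we will have 20 enable and 10 disable", and give 70% power for 30. On allocation, "Block randomization will be used with variable block sizes of three and six".

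**The concern.** If effect size is the primary goal, a rule that can end the trial at half its intended size seems to work against it. At 15 subjects there are about five controls (four or six if a block of six is incomplete). A trial that stops there does so because its observed difference is large, so the estimate is both imprecise and too high. No efficacy look adds power.

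The second worry is that the O'Brien-Fleming boundary depends on the information fraction, which is 15/30 on one reading and 15/42 on the other. An interim p-value between the two boundaries would stop the trial under one reading and not the other. At stake would be the precision of the main result and a stopping decision left to interpretation.

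**Working it through.** **Inputs.** From the plan: two-sided 0.05, one look at 15, 2:1 allocation, 20 v 10 at 30 subjects, 70% power at 30, numbering to 42 (28 v 14 at 2:1). Assumed: a between-arm t-test on pre-post change, equal SDs, 10 v 5 at the look, stopping for efficacy, the classic O'Brien-Fleming boundary, and boundaries applied as t-test p-values.

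**The plan's 70%.** It cannot be reproduced, because no effect size or SD is given. Solving the noncentral t for 70% power at 20 v 10 gives 0.997 SD, so 1.0 SD is the only effect tied to the documents. True effects of 1.5 and 2.0 SD are shown for range.

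**Boundaries.** The classic two-look form has z1 = C/√f and z2 = C, with C solved so that total alpha is 0.05.
- f = 15/30 = 0.50: z 2.797 and 1.977, p 0.0052 and 0.0480.
- f = 15/42 = 0.357: z 3.286 and 1.964, p 0.0010 and 0.0496.

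The version matters too. An O'Brien-Fleming-type spending function at 0.025 per side gives first boundaries of p 0.0031 and 0.00035.

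**Precision by size.** The 95% half-width in SD units is t(0.975, df) × √(1/n1 + 1/n0).
- 10 v 5: 2.160 × 0.548 = 1.18.
- 20 v 10: 2.048 × 0.387 = 0.79.
- 28 v 14: 2.021 × 0.327 = 0.66.

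**Operating characteristics.** Stop probabilities are exact (noncentral t, 13 df); the rest are simulated.

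| | 1.0 SD | 1.5 SD | 2.0 SD |
|---|---|---|---|
| Maximum 30: chance of stopping | 11% | 32% | 62% |
| Mean estimate given a stop (SD) | 1.80 | 2.01 | 2.28 |
| Overall bias | 4% | 6% | 4% |
| Overall 95% CI coverage | 94.2% | 94.9% | 95.2% |
| RMSE (SD), with v without stop | 0.451 v 0.387 | 0.474 v 0.388 | 0.473 v 0.387 |
| Average pairs saved (15 × stop probability) | 1.6 | 4.8 | 9.3 |
| Maximum 42: chance of stopping | 4% | 14% | 36% |
| RMSE (SD), with v without stop | 0.372 v 0.328 | 0.415 v 0.327 | 0.443 v 0.327 |
| Average pairs saved (27 × stop probability) | 1.0 | 3.8 | 9.7 |

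Power at 1.0 SD is 69.9% with the look against 70.3% without (maximum 30), and 84.5% against 84.6% (maximum 42).

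**The 30 or 42 question.** The chance that the two readings disagree on stopping is the difference in unrounded stop probabilities: 0.109 − 0.036, about 7%, at 1.0 SD; 0.323 − 0.140, about 18%, at 1.5 SD; 0.620 − 0.358, about 26%, at 2.0 SD. Under the normal model, type I error is 0.0509 if the 30 boundary is set but the trial runs to 42, and 0.0498 in the reverse case. With the correct maximum and t-test p-values, simulation gives 5.1% and 5.0%.

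**The case for a change.** The strongest case for a change looks at what a reader of a stopped trial receives. At a true 1.0 SD with a maximum of 30, the estimate given a stop averages 80% too high, and the ordinary 95% interval covers the truth in only about 77% of stopped trials (39% with a maximum of 42). Little offsets this. The protocol is minimal risk, the devices are collected afterwards and results are not shared with subjects, so stopping early brings no patient earlier access. Payment is only $50 per pair.

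The exchange is not even at moderate effects either. At 2:1 the squared standard error is 4.5/N. A fixed trial of the same average size at 1.0 SD, 30 − 1.6 = 28.4 pairs, would have a standard error of √(4.5/28.4) = 0.398 SD, against the 0.451 above.

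All of that stands as description. It does not make the rule an error. The conditional distortion falls on the 11% (or 4%) of trials that stop at 1.0 SD. At 2.0 SD, where stopping is common, the inflation given a stop is 14% and overall coverage is 95.2%. Any efficacy look costs precision and adds no power; what it buys is a smaller expected sample. Mask, hose, staff time and transcription are further costs per pair that the plan does not price. Writing out the boundaries and labelling an early-stop result would not cure the conditional bias, because the labelled interval would still cover in about 77% of stopped trials at 1.0 SD.

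One implementation risk is real: z cut-offs applied to t statistics would raise type I error to 6.6% (15/30) or 6.0% (15/42). The plan nowhere directs that.

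**Conclusion.** No change to the plan follows. Keeping or dropping the efficacy stop is a fair trade-off for the sponsor: the plan seeks superiority and effectiveness as well as an effect size, and it sets no precision target that the look would miss. At the effect implied by its own power figure, and with a maximum of 30, the look raises root-mean-square error by about 16%, biases the estimate by about 4% overall, and costs under half a point of power.

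The unfixed maximum is a gap that analysts can fill sensibly. An intended size of about 30, a power statement at 30 and a look at exactly half of 30 agree, and numbering to 42 can be read as the count of prepared envelopes. The wording about randomizing only 30 leaves some doubt, but overall type I error stays near 5% on either reading. The boundary version, its direction and the reporting after a stop are missing details of the same kind. Stating them would be good housekeeping.

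This rests on the assumed t-test on pre-post change, an efficacy stop and the classic boundary. True effects of 1.5 to 2.0 SD would make stopping, and disagreement between the two readings, more frequent, but no passage supports effects of that size. With a maximum of 30, a single test without the look would already have power of about 96% at 1.5 SD and above 99% at 2.0 SD.
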